7.3 Study Conduct

All randomized patients are included in the analyses of study conduct. Information will be tabulated by randomized treatment (unless otherwise indicated) and pooled treatments.

7.3.1 Patient Disposition

- Number of patients randomized, treated (for patients on Durva+Treme arm only: on study, off study), never treated (**Table 1**)
- Number of alive patients (**Table 2**)
- Median (estimated by Kaplan-Meier method) and range (minimum and maximum) (**Table 2**) of the follow-up time (months) defined as time from the day of randomization (as recorded in centralized randomization file) to the last day the patient is known alive (LKA) as the last recorded date known alive or censored at the time of death and calculated as

$$[(\text{date of death or LKA} - \text{date of randomization}) + 1]/30.4375.$$

7.3.2 Accrual Patterns

- Number of patients randomized by center (**Table 3**)
- Number of patients by stratification factors at randomization (**Table 4**)
- Accrual of patients by calendar time pooled across two treatment arms (**Figure 1**)

7.3.3 Eligibility Violations/Protocol Deviations

Eligibility violations of inclusion or exclusion criteria are centrally reviewed by CCTG; a field (y/n) for eligibility status and reason for ineligibility is entered in the database. A major protocol violation (MPV) is defined as a deviation from the protocol, initiated by the centre or the investigator, serious enough to mean that the patient's data contributes little, if any, information on the efficacy or toxicity of the regimen under study. MPVs are coded by CCTG based on its standard codes.

- Number of patients eligible, not eligible (**Table 5**)
- Reasons for ineligibility (**Table 5**)
- Major protocol violations: % for each type of violations (**Table 5**).

Deviations from randomization will be summarized as follows:

- Treatment as randomized versus as treated (**Table 6**)

7.4 Study Population

All randomized patients are included in the study population analyses. Information will be tabulated by randomized treatment (unless otherwise indicated) and pooled treatments.

7.4.1 Patient Pretreatment Characteristics

- Gender (**Table 7**)
- Race (**Table 7**)
- Age: median, minimum, maximum values; number <65, ≥65 (**Table 7**)
- ECOG Performance Status: 0, 1 (**Table 7**)
- BSA: median, minimum, maximum values (**Table 7**)
- Months from first histological diagnosis of colorectal cancer to randomization: median, minimum, maximum values (**Table 7**)
- Histology: adeno-carcinoma, etc. (**Table 7**)
- Site of tumour: right colon, transverse colon, left colon, rectum, unknown (**Table 7**)
- KRAS mutation status: wild-type, mutated, unknown (**Table 7**)
- NRAS mutation status: wild-type, mutated, unknown (**Table 7**)
- BRAF mutation status: wild-type, mutated, unknown (**Table 7**)
- MSI status: MSI-H, MSI-L, MSS, Unknown (**Table 7**)

7.4.2 Prior Surgery

- Number of patients with prior surgery for colorectal cancer (**Table 8**)
- Procedure/site of prior surgery (**Table 8**)

7.4.3 Prior radiotherapy

- Number of patients with prior adjuvant or palliative radiotherapy. (**Table 9**)
- Prior radiotherapy by site and type (adjuvant or palliative) (**Table 9**)

7.4.4 Prior Systemic Therapy

- Number of subjects with prior systemic therapy and type of prior systemic therapy (adjuvant, metastatic, neo-adjuvant) (**Table 10**)
- Number of patients with prior thymidylate synthase inhibitor (**Table 11**)
- Number of patients with prior irinotecan containing regimen (**Table 11**)
- Number of patients with prior oxaliplatin containing regimen (**Table 11**)
- Number of patients with prior cetuximab or panitumumab containing regimen (**Table 11**)
- Number of patients with prior VEGF targeting therapy (**Table 11**)
- Number of patients with prior TAS-102 therapy (**Table 11**)

7.4.5 Extent of Disease

- Number of patients with target lesions, number of target lesions, largest measure, site of target lesions (**Table 12**)

- Number of patients with non-target lesions, number of non-target lesions, site of non-target lesions (**Table 13**)

7.4.6 Baseline Exams

- Baseline signs and symptoms (**Table 14**)
- Baseline hematology: WBC, neutrophils, platelets, hemoglobin, RBC, lymphocytes, monocytes, eosinophils, basophils (**Table 15**)
- Baseline serum chemistry: Total bilirubin, AST, ALT, alkaline phosphatase, LDH, serum creatinine, chloride, sodium, albumin, potassium, calcium, magnesium, ALP, glucose, amylase, lipase, CEA (**Table 16**)
- Baseline Thyroid Function Tests (**Table 17**)
- Baseline Coagulation Tests (**Table 18**)
- Baseline ECG (**Table 19**)
- Baseline urinalysis (**Table 20**)

7.4.7 Concomitant Medications and Major Medical Problems at Baseline

- Number of patients with concomitant medication within 14 days prior to the date of randomization (**Table 21**)
- Number of patients with past or current major medical problems ongoing at baseline (**Table 22**)

7.5 Extent of Exposure to Durvalumab and Tremelimumab

Patients included are those who received at least one dose of durvalumab or tremelimumab as defined in Section 6.

7.5.1 Study Therapy

During a 4 week cycle of protocol treatment, the patients received infusion of durvalumab (1500 mg) on day 1 and tremelimumab (75 mg) on day 1 of cycles 1, 2, 3 and 4 only.

Duration of durvalumab or tremelimumab (in weeks) during the study is defined as follows:

[last date of infusion of durvalumab or tremelimumab – first date of infusion of durvalumab or tremelimumab + 28]/7,

where the first and last date of infusion is taken from Durvalumab Administration or Tremelimumab Administration Section of Treatment Report).

The following variable will be summarized using the data set of all patients treated by durvalumab or tremelimumab:

- Number of patients by cycle of therapy (**Table 23**)
- Total number of cycles of treatment per patient (**Table 24**)
- Total treatment duration of durvalumab or tremelimumab per patient (**Table 25**)

7.5.2 Dose Reduction, Omission, Discontinuation, or IV Rate Decrease or Infusion Interruption to Durvalumab or Tremelimumab

The administration of durvalumab or tremelimumab in a cycle may be modified (reduced, omitted, delayed, and IV rate decreased and infusion interrupted) because of toxicity or other reasons. For each drug, the following variables will be summarized using the data set of all treated patients:

- Number of patients who had all of their drug administrations according to protocol (**Table 26**)
- Number of patients with at least one cycle reduced, omitted, delayed, or IV rate decreased and infusion interrupted (**Table 27**)
- Reason for these dose modifications (**Table 27**)

7.5.3 Cumulative Dose, Dose Intensity and Relative Dose Intensity of Durvalumab or Tremelimumab

The cumulative dose (mg) per patient for each drug is the total dose (mg) the patient received, which is defined as the sum of the actual dose level (mg) over the study (**Table 28**).

The actual dose intensity of a drug (mg/week) per patient is defined as:

$$\text{Actual Dose Intensity} = \frac{\text{Cumulative dose (mg)}}{[\text{last dosing date} - \text{first dosing date} + 28]/7}$$

where first and last dosing date is taken from Durvalumab Administration or Tremelimumab Administration Section of Treatment Report (**Table 29**).

The relative dose intensity of durvalumab or tremelimumab per patient is defined as the dose intensity (mg/week) divided by the planned weekly dose as assigned in the protocol, which is 375 mg/week for durvalumab and 18.75 mg/week for tremelimumab.

The patient relative dose intensities will be grouped according to the following categories: < 60%, ≥ 60% - < 80%, ≥ 80% - < 90%, ≥ 90% (**Table 30**).

7.5.4 Off Study Therapy

The reason for off of each study therapy will be taken from End of Treatment Section of End Of Treatment Report.

The following information will be summarized for each of protocol treatment (**Table 31**):

- Number of patients off study treatment
- Reason off protocol therapy

7.6 Efficacy

7.6.1 Overall survival

For all randomized patients, survival is calculated from the day of randomization (as recorded in Centralized Randomization File) to death (Date/Cause of Death Section of Death Report). For alive patients, survival is censored at the last day the patient is known alive (LKA) as the last recorded date known alive (Date of Attendance/Last Contact on Best Support Care Report, 4-Week Post Treatment Report, Follow-up Report, Short Follow Up Report, and Minimal Follow-up Report; or last date of infusion of durvalumab or tremelimumab in Treatment Report). Survival time (in months) is defined as

$$[(\text{date of death or LKA} - \text{date of randomization}) + 1]/30.4375.$$

A frequency table for the number of patients who died and cause of death in each treatment arm will be provided (**Table 32**). Kaplan-Meier curve for proportions of survival in each treatment arm will be displayed (**Figure 2**).

The comparison of overall survival between the two treatment arms is the primary objective of this study. The primary analysis will be the log-rank test (**Table 33**) stratified by the factors coded as:

Stratification Factors (at randomization)

Performance status	1 = ECOG 0	0 = ECOG 1
Site of tumour	1=right colon; 2=transverse colon; 3=left colon; 4=rectum; 5=unknown	

The hazard ratio of durvalumab and tremelimumab combined with best supportive care (ARM 2) over best supportive care alone (ARM 1) and two-sided 90% CI will be calculated (**Table 33**) based on the Cox regression model stratified by above stratification factors, and with treatment arm coded as ARM 2=1 and ARM 1=0. The 90% confidence intervals for the median survival will be computed using the method of Brookmeyer and Crowley [2].

In order to assess the influence of the potential prognostic factors shown and coded below on the comparison of survival between treatment arms, a stratified Cox regression model will be used with all variables (treatment arm and prognostic factors) included to estimate hazard ratios and 90% confidence intervals (**Table 33**).

Prognostic factors (at baseline)

Gender	0 = Female	1 = Male
Age	0 = ≥ 65	1 = < 65
Number of organ sites	0 = > 2	1 = ≤ 2
Presence of liver metastases	0 = Yes	1 = No

No interactions will be considered in the model.

7.6.2 Overall Survival by Subsets

For each level of the following baseline variables, a Kaplan-Meier plot of survival by treatment arm will be produced as well as medians with 90% C.I. and the hazard ratio (unstratified) with 90% CI of durvalumab or tremelimumab combined with best supportive care (ARM 2) over best supportive care alone (ARM 1) (**Table 34**):

- Gender: male, female
- Age: <65, ≥65
- Race: white, black, other
- Performance status at baseline: ECOG 0, 1
- Site of tumour: right colon, transverse colon, left colon, rectum, unknown
- KRAS status: wildtype, mutated
- NRAS status: wildtype, mutated
- BRAF status: wildtype, mutated
- MSI status: MSI-H, MSI-L, MSS

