1.3 Tertiary Objectives

- To determine the effect on quality of life (QoL) of the combination of durvalumab and tremelimumab and best supportive care *versus* best supportive care only in patients with refractory, advanced colorectal cancer.
- To determine the effect of tumour PD-L1 expression assessed by IHC on efficacy of the combination of durvalumab and tremelimumab and best supportive care *versus* best supportive care only in patients with refractory, advanced colorectal cancer.
- To explore association between putative biomarkers in archival tumour specimens and the potential for clinical benefit between the combination of durvalumab and tremelimumab and best supportive care *versus* best supportive care only in patients with refractory, advanced colorectal cancer.
- To explore association with baseline values and changes in putative biomarkers in blood, serum and plasma and the potential for clinical benefit between the combination of durvalumab and tremelimumab and best supportive care *versus* best supportive care only in patients with refractory, advanced colorectal cancer.

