13.2 Study Endpoints and Analysis

Overall Survival:

Overall Survival, the primary endpoint of this study, is defined as the time from randomization to death from any cause. Patients who are alive at the time of the final analysis or who have become lost to follow-up will be censored at their last date known to be alive. Patients will be analyzed in the arm to which they are randomized regardless of the treatment they received (intent-to-treat analysis). The survival experience of patients in both treatment groups will be summarized by the Kaplan-Meier method and compared primarily by a stratified log-rank test adjusting for the stratification variable (ECOG performance status and site of tumour) at randomization. Secondary analyses based on stratified Cox proportional hazards model will also be performed. ECOG performance status (0 versus 1) and site of tumour (right colon, transverse colon, left colon, rectum, unknown) will be the stratification factors to define the stratified Cox proportional hazards model. Besides the treatment factor (combination of durvalumab and tremelimumab + BSC versus BSC alone), the following factors at patient entry will be included in the stratified Cox proportional hazards model:

- Age (< 65 versus \geq 65)
- Sex (male versus female)
- Number of organ sites involved at baseline (\leq 2 versus $>$ 2)
- Presence of liver metastases (yes versus no)

A formal pre-planned subset analysis for the primary endpoint (OS) will be conducted to address the benefit of combination of durvalumab and tremelimumab between the groups defined by the above factors and the following:

- ECOG Performance Status (0 versus 1)
- Race (white, black, Asian, other)
- Site of tumour: (right colon, transverse colon, left colon, rectum)

Progression-Free Survival:

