13.3 Sample Size and Duration of Study

The study is designed to have a power of 80% and a two-sided alpha of 10% to detect a 35% reduction in the continuous risk of death (HR 0.65, which corresponds to an increase of median survival from 4.5 to 6.9 months). It is estimated that 150 events will be required to detect this reduction. The final analysis will be performed when 150 events are observed. Assuming an accrual rate of around 10 patients per month, the required number of events would be observed by accruing a total of 180 patients and following them for a minimum of 6 months. The total duration of the trial would be around 24 months.

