7.6.4 Progression-free survival by Subsets

Subset analyses performed for overall survival will also be performed for PFS (**Table 37**).

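### The OS and PFS subset analyses give a separate hazard ratio for each level but no pre-specified comparison between levels

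*SAP*

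**What the plan says.** Protocol 13.2 announces a formal, pre-planned subset analysis of OS, "to address the benefit of combination of durvalumab and tremelimumab between the groups defined by the above factors" and by ECOG status, race and tumour site. The factors listed above that sentence are age, sex, number of organ sites and presence of liver metastases. The same section says that the OS analyses are repeated for PFS.

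SAP 7.6.2 carries this out level by level. Each level gets a Kaplan-Meier plot and "medians with 90% C.I. and the hazard ratio (unstratified) with 90% CI". SAP 7.6.4 adds: "Subset analyses performed for overall survival will also be performed for PFS". Tables 34 and 37 have columns for the patient numbers, the medians and one unstratified hazard ratio per row. They have no column for an interaction, a ratio of hazard ratios or a p-value.

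The SAP factor list is not the Protocol's. It adds KRAS, NRAS, BRAF and MSI status and omits number of organ sites and liver metastases. Its 7.6.2 text includes an unknown tumour-site level that Tables 34 and 37 leave out. SAP 7.6.6 says that the response subgroups will not be formally compared; 7.6.2 and 7.6.4 carry no such label.

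**The concern.** Whether benefit differs between groups is a question about a contrast between two hazard ratios. A list of within-level hazard ratios with 90% intervals does not state that contrast. It invites the reader to note which intervals exclude 1 and to treat a mixed pattern as evidence that one group benefits and another does not. A level's interval depends on its number of deaths as well as on the effect, so mixed patterns are common even when the effect is the same everywhere. At stake are the subset statements made from this trial, not its primary result.

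**Working it through.** **Inputs.** Protocol 13.3 gives "a power of 80% and a two-sided alpha of 10% to detect a 35% reduction in the continuous risk of death". The target hazard ratio is therefore 0.65, with planning medians of 4.5 months on control and 6.9 months on the combination. On the number of deaths the section states: "It is estimated that 150 events will be required to detect this reduction". Allocation is 2:1, so the information on the log hazard ratio from d deaths is about d × (2/3)(1/3) = 2d/9. The split of deaths between levels is not given and is assumed below. The formulas ignore stratification.

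**The plan's own figure.** Required deaths = (1.645 + 0.842)² / [(2/9)(ln 0.65)²] = 149.9, or 150. The Protocol's number is reproduced.

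**Number of hazard ratios.** Table 34 rows, in order: ECOG 2, age 2, gender 2, race 3, site 4, KRAS 2, NRAS 2, BRAF 2, MSI 3. The sum is 22, and Table 37 has the same 22. The 7.6.2 text lists 23 because of the unknown site.

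**Reading two levels separately when the effect is the same in both (HR 0.65).**
- With 75 deaths, SE of the log hazard ratio = 1/√(75 × 2/9) = 0.245. The expected 90% interval is 0.65 × exp(±1.645 × 0.245) = 0.43 to 0.97.
- P(the interval lies below 1) = Φ(0.431 × √16.67 − 1.645) = Φ(0.114) = 0.545.
- The two levels contain different patients, so P(exactly one does) = 2 × 0.545 × 0.455 = 0.496.

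Sensitivity to the assumed split, with HR 0.65 throughout:

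| Deaths per level | P(interval below 1), larger / smaller | P(exactly one) |
|---|---|---|
| 75 / 75 | 0.545 / 0.545 | 0.50 |
| 100 / 50 | 0.650 / 0.417 | 0.52 |
| 120 / 30 | 0.719 / 0.297 | 0.59 |

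At a 75/75 split and a weaker common effect of HR 0.80, each probability is Φ(0.223 × 4.082 − 1.645) = 0.23 and P(exactly one) is 0.36. A treatment-by-factor test at 10% would flag a difference in 10% of such trials.

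**What an interaction analysis could detect.**
- At an even split, SE of the log ratio of hazard ratios = √(1/16.67 + 1/16.67) = 0.346.
- Ratio detectable with 80% power at two-sided 10%: exp(−2.487 × 0.346) = 0.42, or 2.37 in the other direction.
- Power for a ratio of 0.65: Φ(0.431/0.346 − 1.645) = 0.34.
- For MSI-H, which Protocol 2.0 puts below 5% of such patients (fewer than 9 of 180), a 5/95 split of deaths gives SE 0.795 and a detectable ratio of 0.14.

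**Multiplicity of those tests.** The SAP has nine factors. If the tests were independent, P(at least one false positive at 10%) = 1 − 0.9⁹ = 0.61. With the two omitted Protocol factors restored there are eleven, and 1 − 0.9¹¹ = 0.69.

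**The case against.** The best defence is that SAP 7.6.2 plans estimation only. It sets no p-value and no significance rule, so the 50% describes a misreading that the SAP does not prescribe. The Protocol sentence is loosely worded and names no test. Levels of one factor share no patients, so a reader can form the ratio of two tabulated hazard ratios and its interval by hand. Interaction tests would be weak and numerous, and a descriptive label like the one in SAP 7.6.6 would be simpler.

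Much of this stands. The comparison is recoverable, so a claim that the plan cannot answer its own question would go too far. What is missing is its pre-specification and presentation. The points on power and multiplicity are right and shape the fix. A descriptive label alone would stop the misreading, but it would leave the Protocol calling the analysis formal while nothing compares the groups.

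Four stronger readings are tempting, and the documents do not support them:
- *The SAP rules out interactions altogether.* The sentence "No interactions will be considered in the model" closes the account of the prognostic-factor Cox model in 7.6.1. It does not govern 7.6.2.
- *Apparent subset differences will mostly be noise.* That assumes one common effect. Protocol 2.0 reports an OS hazard ratio of 0.22 for MSI-H against MSI-S in a pembrolizumab trial. That compares MSI groups, not treatments, but it makes a real MSI difference plausible.
- *Subset results will guide later patient selection.* Neither document says so; Protocol 2.0 frames the question regardless of MSI status.
- *PD-L1 has been wrongly left out of the subset list.* It belongs to a separate tertiary objective ("To determine the effect of tumour PD-L1 expression assessed by IHC on efficacy of the combination"), rests on a correlative tissue assay, and has no stated cut-off. Protocol 13.2 does not list it.

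**Conclusion.** The gap is real and limited. The Protocol describes a formal subset analysis of benefit between groups; the SAP delivers 22 within-level hazard ratios per endpoint and no planned comparison between them. The Protocol attaches the word formal to OS only, and PFS follows through its general sentence on repeating the OS analyses.

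The size of the risk is about a 50% chance per two-level factor of a one-sided pattern under a common hazard ratio of 0.65. It rests on an assumed even split of deaths, 2:1 allocation within each level and the usual large-sample approximation. It is somewhat higher for uneven splits and lower for a weaker effect (0.36 at HR 0.80). It is a statement about how the tables may be read. It does not predict that any particular difference seen will be false. An interaction analysis would match the stated aim and show the uncertainty openly, but it would not supply the power that 150 deaths lack.

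**What to change.** In SAP 7.6.2 and 7.6.4:
1. For each factor, fit one Cox model with treatment, factor and treatment-by-factor, stratified by ECOG status and tumour site. Drop the stratifier when it is itself the factor.
2. Add two columns to Tables 34 and 37. The first is the interaction p-value, a global test where a factor has three or more levels. The second is the ratio of hazard ratios against a stated reference level, with 90% CI. Footnote that this ratio is stratified and need not equal the quotient of the unstratified row values.
3. Label these results exploratory, unadjusted for multiplicity and low-powered, giving the figures above. State that intervals excluding 1 in some levels and not in others are not evidence of differential benefit.
4. Restore number of organ sites and liver metastases as Protocol 13.2 requires. Reconcile the unknown site level between text and tables, and the race categories, where the Protocol lists Asian separately and the SAP does not.

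PD-L1 is outside this change. The cost is a few model statements, two table columns and a paragraph of text. Organ sites and liver metastases are already covariates in SAP 7.6.1, so no new data are needed. The primary analysis and the sample size do not change. The drawback is a set of weak, multiple tests, which the exploratory label has to make plain.

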7.6.3 Progression-free Survival

Progression-free survival (PFS) will be calculated for all patients from the day of randomization until the first observation of disease progression (date of objective relapse or progression of Relapse/Progression Report) or death due to any cause (recorded in Date/Cause of Death Section of Death Report) as the (difference+1).

If a patient has not progressed or died, PFS will be censored on the date of last disease assessment defined as the earliest test date of target lesion or non-target lesions (if patient has no target lesions), whichever is latest.

A frequency table will be provided describing progression and censoring as follows (**Table 35**):

- Number of patients who progress (documented progression, death without documented progression)
- Number of patients censored (alive and not progressed)

Analyses for PFS will be similar to that for overall survival as previously described. A Kaplan-Meier curve for PFS in each treatment arm will be displayed (**Figure 3**). In the primary analysis, median PFS for the two treatments will be compared using the stratified log-rank test (**Table 36**). A stratified Cox regression model will estimate the durvalumab and tremelimumab combined with best supportive care (ARM 2) over best supportive care alone (ARM 1) PFS hazard ratio and 90% C. I. (**Table 36**). In addition, a stratified Cox regression model adjusted for covariates will be applied to verify the impact of the prognostic factors on the treatment effect (**Table 36**).

Coding for treatment arm, stratification variables and prognostic factors is identical to that presented in **Section 7.5.1**.

Some patients received other anti-cancer therapy before progression or death. Sensitivity analyses will be performed by censoring those who have received anti-cancer therapy prior to documentation of disease relapse/progression or death on the earliest date cancer treatment began or treating them as having PFS events at the earliest date when the treatment began.

